- Patients on Medicare Advantage or HMO plans cannot be analyzed because Medicare data do not contain comprehensive claims records for these patients, who make up 32% to 42% of the Medicare population, with higher uptake in certain geographic regions, potentially affecting generalizability of our findings.
- The planned survival analysis will be based on an intent-to-treat approach, regardless of changes to their exposure status during the follow-up, which may influence the survival outcome.
- Because the treatment regimens will be defined using a claims-based algorithm, it is reasonable to assume some risk of misclassification—even though the algorithm rules will be drawn from previously published methods.

The SEER-Medicare database used for this study, however, remains a unique—and the most authoritative—data source to examine survival outcomes in older patients with diagnosis of cancer at the US Medicare population level.

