2.1 STUDY DESIGN

[figure not shown]
This study will encompass a retrospective cohort analysis using clinical and administrative claims data from the linked SEER-Medicare database (providing SEER data are available through 2019 and linked Medicare claims are available through 2020) for patients with diagnosis of HR+/HER2- mBC at initial presentation. The study will assess the rates of OS in patients 65 years or older with diagnosis of *de novo* mBC from 2015-2019 who initiated 1L systemic therapy with palbociclib + AI or AI alone following the first approval of palbociclib in February 2015. **Figure 2-1** presents a graphical schema of the study design (drawn for a hypothetical patient and not to scale).

Based on the study schema presented below, the following key study definitions will apply:

- **De novo mBC diagnosis date window:** From 1 February 2015 through 31 December 2019
- **Study index date:** The date of 1L treatment initiation with palbociclib + AI or AI alone after the *de novo* mBC diagnosis
- **Case selection window:** From 1 February 2015 through 30 June 2020 – for the date of 1L treatment initiation (study index date)

- **Baseline period:** The 6-month period before the study index date (to assess patient baseline demographic and clinical characteristics)
- **Study follow-up:** All patients will be followed from their study index date through the earliest of the following: death, disenrollment from Medicare Part A (hospital insurance), Part B (medical insurance), or Part D (prescription drug insurance), enrollment in a health maintenance organization (HMO) plan, or end of the study database (31 December 2020).
- **Overall study period:** From 1 August 2014 (to allow up to 6 months of look back period for any patient with index date in February 2015) through 31 December 2020 (accounting for a minimum 6 months of potential follow-up for any patient with index date in June 2020).

Figure 2-1. Study Design Schematic (Depiction for a Hypothetical Patient)

AI = aromatase inhibitor; HER2- = human epidermal growth factor receptor 2-negative; HR+ = hormone receptor-positive; mBC = metastatic breast cancer.

Note: Figure not drawn to scale.

Study Population

The study population will represent Medicare beneficiaries (men or women) with diagnosis of HR+/HER2- mBC at initial presentation (i.e., de novo), as identified in the SEER-Medicare database.

Data Source

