8. *Continuously enrolled in Medicare Parts A and B with no HMO participation for ≥ 6 months before the index date*
 - *Because HMOs are not obligated to provide information about healthcare encounters (i.e., administrative procedure and diagnosis codes) to the Medicare system, patients who were enrolled in an HMO during study period may have incomplete data on service utilization, which may affect the accuracy of measurement for comorbid conditions and receipt of systemic therapy lines.*

Exclusion Criteria

Patients will be excluded if their mBC diagnosis was first recorded in a death certificate or at the time of autopsy.

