5.4 STUDY ENDPOINTS

The endpoints or study outcomes to be analyzed for each study objective and the associated definitions are described in [Table 5-1](#).

Table 5-1. Definition of Endpoints

Variable	Role/objective	Definition
Overall survival in 1L	Primary	The time in months from initiation of 1L therapy (palbociclib + AI or AI alone) to all-cause death . Patients who did not die will be censored at the end of study follow-up as defined in Section 2.1 .
CCI		[REDACTED]

Variable	Role/objective	Definition
CCI		
Time to chemotherapy	Exploratory	Time in months from the study index date to first initiation of chemotherapy in any subsequent therapy lines. Patients who did not initiate chemotherapy treatment as of last follow-up will be censored at the end of the follow-up.

1L = first line; AI = aromatase inhibitor; CDK4/6 = cyclin-dependent kinase 4 and 6;

CCI

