PSM: In the PSM technique, each patient in the palbociclib +AI cohort will be matched to a patient in the AI alone cohort using a 1-to-1 matching with no replacement, using the nearest neighbor method to match by closest propensity scores (with a caliper of 0.01). As described above, median OS, landmark probabilities of event at various timepoints, and 95% CI for the matched cohorts will be assessed, and the hazard ratio will be assessed using the univariate CPH model. To plot survival functions and to test for differences between AI + palbociclib and AI alone, the Kaplan-Meier estimator will be used. Given the matched nature of the study cohorts, the CPH analysis will use a robust variance estimator to account for the clustering within paired sets.

All patients will be followed from the start of therapy line through the earliest of the following: death; disenrollment from Medicare Parts A, B, or D; enrollment in an HMO plan; or end of the study database (31 December 2020). Section 7.6 discusses potential sensitivity analyses (e.g., adjusting for subsequent treatments received).

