7.6 SENSITIVITY ANALYSES

*To test for the robustness of the results for the primary objective, sensitivity analyses will be performed using multivariable CPH analysis and PSM as described earlier in Section 7.3. Another sensitivity analysis may be performed for a subset of patients who initiated their 1L therapy within 3 months of *de novo* mBC diagnosis (vs. within 6 months of diagnosis as planned for the main analysis). Additionally, a sensitivity analysis may be considered to adjust for subsequent treatment with CDK4/6 inhibitors using methods such as the Rank Preserving Structural Failure Time (RPSFT) (Robins et al., 1991). Further, considering that the information on patients vital status is up to date and complete as of the end of study period (Dec 2020), the definition of the end of study follow-up may be revisited to disregard the criteria of continuous enrollment in Medicare Parts A, B, and D and enrollment in an HMO; consequently, a sensitivity analysis may be performed to examine if changing this definition has any effect on the OS endpoint.*

In the sensitivity analysis involving adjustment for patients on AI monotherapy who switch to palbociclib + AI combination, the following strategies may be considered (Kang et al., 2022):

PFIZER CONFIDENTIAL

- **Estimand strategy:** Take the hypothetical strategy for the intercurrent event of “treatment switch” as if subsequent treatment with CDK4/6 inhibitors in the AI monotherapy cohort during any time of the observation period had not occurred.
- **Intercurrent events:** All data will be used regardless of the occurrence of intercurrent events (concomitant or subsequent treatments) except for the use of CDK4/6 inhibitors in the AI monotherapy cohort as a subsequent treatment.
- **Population-level summary:** Summary of OS adjusting for subsequent CDK4/6 inhibitors will be provided. After RPSFT, primary analyses will be repeated with modified survival times for the patients who switched from AI monotherapy to palbociclib + AI combination.

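### Primary overall survival is censored when Medicare coverage changes, although the SAP says deaths are known completely to December 2020

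*SAP*

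**What the plan says.** SAP 2.1 follows each patient from index to the earliest of death, "disenrollment from Medicare Part A (hospital insurance), Part B (medical insurance), or Part D (prescription drug insurance"), HMO enrollment, or 31 December 2020. SAP 7.3 repeats the rule for the primary analysis ("disenrollment from Medicare Parts A, B, or D; enrollment in an HMO plan; or end of the study database"), and Protocol 9.1 carries the same definition. Table 5-1 in SAP 5.4 defines OS as time to all-cause death, with survivors "censored at the end of study follow-up as defined in Section 2.1". The rule is therefore consistent across sections.

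The data-source text in SAP 2.1 says death dates come from the Social Security Administration, the Railroad Retirement Board and the Medicare Common Working File. It says they are complete for the enrollment year, including 2020, and that 99% of deaths are validated. SAP 7.6 raises the alternative of ignoring the enrollment criteria, "considering that the information on patients vital status is up to date and complete as of the end of study period (Dec 2020"). It leaves that analysis optional: "a sensitivity analysis may be performed to examine if changing this definition has any effect on the OS endpoint". Protocol 9.7.3 says the same.

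In SAP 4.1, the reason for excluding HMO participation is that such patients "may have incomplete data on service utilization, which may affect the accuracy of measurement for comorbid conditions and receipt of systemic therapy lines".

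**The concern.** A coverage change stops the claims record, but on the documents' own account it does not stop the death record. Comorbidity is measured before index and first-line therapy shortly after it, so later gaps in claims affect subsequent-line variables and not all-cause death. No reason is given for making the enrollment-censored version primary.

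Two things are at stake.

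- **Precision.** Known deaths are discarded.
- **Informative censoring.** If patients who leave have a different prognosis from those who stay, and leaving differs by arm, the hazard ratio can shift. The planned stabilized weights model treatment assignment only, and no censoring weights are planned. The multivariable Cox sensitivity analysis would handle exit that depends on measured baseline covariates, but not exit driven by unmeasured or later prognosis.

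Because full follow-up is optional, the report might never show whether the choice mattered.

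**Working it through.** The plan states no sample size, event count or rate of coverage change, so it has no figure to reproduce. What follows is an illustration.

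**Inputs from the documents**
- Index dates run from 1 February 2015 to 30 June 2020 and the data end on 31 December 2020. Potential follow-up C is therefore about 6 to 71 months, taken as uniform.
- Median OS of 43.2 and 49.1 months and a hazard ratio of 0.76 (95% CI 0.65–0.87) come from the Flatiron study cited in SAP 2.
- The 95% CI of 0.42–0.82 comes from the earlier SEER-Medicare study cited there.

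**Assumed**
- Exit from coverage of 2, 4, 6 or 8% per year, as a constant monthly hazard g = rate/12.
- Exponential survival, with l = ln 2 / median.

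**Deaths counted**
- Full follow-up: mean over C of 1 − exp(−lC).
- Censored at exit: mean over C of [l/(l+g)] × [1 − exp(−(l+g)C)].
- Widening of the CI for the log hazard ratio: √(full/censored).

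At a median of 43.2 months, l = 0.01605 and full follow-up captures a death in 0.4361 of patients. At 49.1 months, l = 0.01412 and the figure is 0.3987.

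| Exit per year | 43.2 mo: censored | Deaths lost | CI factor | 49.1 mo: censored | Deaths lost | CI factor |
|---|---|---|---|---|---|---|
| 2% | 0.4221 | 3.2% | 1.016 | 0.3857 | 3.3% | 1.017 |
| 4% | 0.4089 | 6.2% | 1.033 | 0.3733 | 6.4% | 1.034 |
| 6% | 0.3963 | 9.1% | 1.049 | 0.3615 | 9.3% | 1.050 |
| 8% | 0.3843 | 11.9% | 1.065 | 0.3503 | 12.1% | 1.067 |

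Example at 4% and 43.2 months: 1 − 0.4089/0.4361 = 6.2%, and √(0.4361/0.4089) = 1.033.

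**Hazard ratio.** This was simulated with unweighted Cox models in 1,000,000 patients. The death hazard carried a log-normal frailty exp(0.8z), or none, and the exit hazard was multiplied by exp(+0.8z), exp(−0.8z), or 1. The true hazard ratio was 1.00 or 0.76. Ratio of the enrollment-censored to the full-follow-up hazard ratio:

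| Exit pattern | Ratio |
|---|---|
| Not prognostic, equal or unequal by arm | 0.997–1.002 |
| Prognostic, 4% per year in both arms | 0.992–1.001 |
| Prognostic, 3% vs 6% per year | 0.968–1.024 |
| Prognostic, 3% vs 8% per year | 0.953–1.039 |

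With a true hazard ratio of 1.00 and 3% vs 8% exit, the ratio is 0.964 or 1.039, a log shift of 0.037–0.038.

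**Scale of that shift.** The SE from the SEER-Medicare interval is ln(0.82/0.42)/3.92 = 0.171, so the shift is 0.037/0.171 ≈ 0.2 SE. The SE from the Flatiron interval is ln(0.87/0.65)/3.92 = 0.074, so it is 0.038/0.074 ≈ 0.5 SE.

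**Medians.** SAP 7.3 also reports median OS and landmark probabilities, and these can move even when exit is equal by arm. In the frailty model, at 4–8% exit per year, a median of about 40.6 months became about 42.6–44.4 or 37.4–38.8, depending on which patients leave. With non-prognostic exit it did not move.

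**The case against.** The plan sees the issue. SAP 7.6 and Protocol 9.7.3 describe the alternative and give the reason for it. What remains is which of two described analyses is primary, and whether the other is optional. That is fair, but an optional analysis can be left out after results are known, and no argument supports the present order.

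Protocol 9.9 states: "The planned survival analysis will be based on an intent-to-treat approach, regardless of changes to their exposure status during the follow-up". That sentence concerns treatment changes, not insurance, so enrollment censoring does not contradict it. This stands; the case does not need it.

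No harm is demonstrated. Every size above rests on assumed exit rates, and the hazard ratio moves noticeably only under two further assumptions together. This also stands and limits the weight of the point.

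Full follow-up is not automatically closer to a treatment effect net of coverage change. If the coverage change itself raised mortality, the censored estimate could be nearer to that quantity. In runs with an input hazard ratio of 0.76, a death hazard that doubles after exit, and exit of 10% (AI alone) vs 3% (palbociclib), the results were 0.708 full and 0.768 censored. With the rates reversed they were 0.840 and 0.772. Which is wanted depends on the estimand, and the plan states all-cause death without setting coverage changes aside.

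Finally, the fix splits the observation window. SAP 7.6 says: "After RPSFT, primary analyses will be repeated with modified survival times for the patients who switched". RPSFT (the rank preserving structural failure time analysis) needs claims to see later CDK4/6 inhibitor use, so it could no longer simply repeat the primary analysis. This is a real but manageable cost.

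**Conclusion.** The concern holds. The primary OS analysis discards deaths that the SAP says are known, for a reason that applies only to claims-based variables, and the analysis that would keep them is optional.

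The established consequence is lost precision, whose size depends on the exit rate: about 3–12% of deaths and a CI 1.6–6.7% wider at an assumed 2–8% exit per year. Bias in the hazard ratio is possible but not shown. If exit is unrelated to prognosis or equal by arm, the ratio of censored to full hazard ratio stays at about 0.99–1.00. Only if exit is both prognostic and unequal does a null hazard ratio move to about 0.96–1.04, with unknown direction. This should be fixed because the remedy is cheap, not because a large distortion has been demonstrated.

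**What to change.** - **SAP 2.1 and 7.3, and Protocol 9.1:** define primary OS follow-up as index date to death from any cause or 31 December 2020, regardless of later Part A, B, D or HMO status. The OS row of Table 5-1 then follows by its cross-reference.
- **SAP 7.6 and Protocol 9.7.3:** make the enrollment-censored OS analysis a sensitivity analysis that is always performed.
- **Reporting:** give the number, type (A/B, D, HMO) and timing of coverage exits by arm.
- **Claims-based analyses:** keep enrollment censoring for time to chemotherapy, other claims-based outcomes and RPSFT, each with its own stated end of follow-up. Reword the RPSFT text so that its result is compared with the enrollment-censored OS result, and both use one window.

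The change swaps two analyses already described and needs no new data. It does need a protocol amendment to match the SAP. RPSFT and time to chemotherapy will use a shorter window than primary OS: at 2–8% exit per year, about 3–12% of post-index survival time falls after exit (under a constant death hazard, the same share as deaths lost). If the sponsor prefers to keep the present primary definition, the minimum is to justify it, make the full-follow-up analysis mandatory, and report exits by arm.

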7.4 ANALYSES FOR EXPLORATORY OBJECTIVES

Exploratory study measures CCI

7.5 SUBGROUP ANALYSES

Further, to help better explain the results and to generate additional contextual data, subgroup assessments may be performed according to age groups, race/ethnicity, comorbidity score, metastatic sites, dual Medicare/Medicaid eligibility, and other patient characteristics as appropriate and based on availability of the data and adequate sample sizes.

7.6 SENSITIVITY ANALYSES

*To test for the robustness of the results for the primary objective, sensitivity analyses will be performed using multivariable CPH analysis and PSM as described earlier in Section 7.3. Another sensitivity analysis may be performed for a subset of patients who initiated their 1L therapy within 3 months of *de novo* mBC diagnosis (vs. within 6 months of diagnosis as planned for the main analysis). Additionally, a sensitivity analysis may be considered to adjust for subsequent treatment with CDK4/6 inhibitors using methods such as the Rank Preserving Structural Failure Time (RPSFT) (Robins et al., 1991). Further, considering that the information on patients vital status is up to date and complete as of the end of study period (Dec 2020), the definition of the end of study follow-up may be revisited to disregard the criteria of continuous enrollment in Medicare Parts A, B, and D and enrollment in an HMO; consequently, a sensitivity analysis may be performed to examine if changing this definition has any effect on the OS endpoint.*

In the sensitivity analysis involving adjustment for patients on AI monotherapy who switch to palbociclib + AI combination, the following strategies may be considered (Kang et al., 2022):

PFIZER CONFIDENTIAL

- **Estimand strategy:** Take the hypothetical strategy for the intercurrent event of “treatment switch” as if subsequent treatment with CDK4/6 inhibitors in the AI monotherapy cohort during any time of the observation period had not occurred.
- **Intercurrent events:** All data will be used regardless of the occurrence of intercurrent events (concomitant or subsequent treatments) except for the use of CDK4/6 inhibitors in the AI monotherapy cohort as a subsequent treatment.
- **Population-level summary:** Summary of OS adjusting for subsequent CDK4/6 inhibitors will be provided. After RPSFT, primary analyses will be repeated with modified survival times for the patients who switched from AI monotherapy to palbociclib + AI combination.

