IPTW: The general approach for an IPTW analysis involves calculating the inverse probability weights and then using these weights to estimate the treatment effect. The IPTW for each patient is the inverse of their PS for their respective treatment group. For exposed individuals, the weight is $1/PS$, and for unexposed individuals, it is $1/(1 - PS)$. The treatment weights derived from the PSs might be large because patients receiving palbociclib + AI treatment may have PSs closer to 0, while patients receiving AI monotherapy may have scores closer to 1. Consequently, extreme weights and inflated variance can occur. To mitigate this potential problem, we will calculate sIPTW, as suggested by Pezzi et al. (2016), Xu et al. (2010), and Shiba and Kawahara (2021). By employing sIPTW, the point estimates of the treatment effect will remain unaffected compared with unstabilized weights while leading to a more accurate estimation of the variance. Once the stabilized inverse probability weights are calculated for each individual, they will be used to estimate the average treatment effect by comparing the weighted outcomes between the treatment (palbociclib + AI) and control (AI alone) groups. For Kaplan-Meier analysis, sIPTW will be applied to assess weighted median OS and 95% CI; weighted survival curves will be drawn and weighted landmark probabilities of event at various timepoints will be estimated (e.g., 12 months and 24 months). For assessing weighted estimate of hazard ratio for the treatment type (AI + palbociclib vs. AI alone), sIPTW will be applied to the Cox proportional hazards model. Variance will be estimated using robust variance estimation method to account for the weighted nature of the data. Point estimate (i.e., hazard ratio) will be derived along with 95% CI; any covariates with residual imbalance may be adjusted for in this step.

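### If RPSFT is used, SAP 7.6 repeats the weighted Cox model as though the estimated acceleration factor were known, so its 95% CI is too narrow; with no re-censoring rule, the hazard ratio can also be biased in either direction

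*SAP*

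**What the plan says.** SAP 7.6 introduces the analysis as optional: "a sensitivity analysis may be considered to adjust for subsequent treatment with CDK4/6 inhibitors using methods such as the Rank Preserving Structural Failure Time". Its target is hypothetical, survival "as if subsequent treatment with CDK4/6 inhibitors in the AI monotherapy cohort during any time of the observation period had not occurred". If RPSFT is run, the next step is stated firmly: "After RPSFT, primary analyses will be repeated with modified survival times for the patients who switched from AI monotherapy" to palbociclib + AI.

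The primary analysis to be repeated is the stabilized-weight (sIPTW) Kaplan-Meier and Cox analysis of SAP 7.3. The variance rule for that Cox model is: "Variance will be estimated using robust variance estimation method to account for the weighted nature of the data". For overall survival, SAP Table 5-1 says: "Patients who did not die will be censored at the end of study follow-up". SAP 2.1 defines that end: "All patients will be followed from their study index date through the earliest of the following: death, disenrollment from Medicare Part A", or loss of Part B or D, HMO enrollment, or the database end on 31 December 2020.

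Neither document says how the acceleration factor is estimated, whether counterfactual times are re-censored, or whether the interval reflects uncertainty in the factor.

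**The concern.** There are two separate problems.

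**The interval.** RPSFT first estimates an acceleration factor from the same data and then uses it to rewrite the switchers' times. A Cox model fitted afterwards takes those rewritten times as observed. The SAP 7.3 robust variance covers the weighting step and nothing else, so a literal repeat leaves out one source of error.

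**The point estimate.** If palbociclib prolongs life, a switcher's time after the switch is shrunk, and this includes censored time. Two AI-alone patients with the same follow-up then have different censoring times according to whether and when they switched. If switching is related to prognosis, that censoring is informative. The standard remedy, re-censoring, changes the times of non-switchers too, whereas SAP 7.6 mentions modified times only for switchers.

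RPSFT is the only adjustment method for switching that the plan names, and its result would be read as the effect without crossover. An interval more favorable than the intent-to-treat one could be an artifact of the variance rule.

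**Working it through.** **Plan's own figure.** There is none to reproduce. The documents give no sample size (Protocol 9.5), event count, switching share or RPSFT quantity.

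**Inputs from the documents.** Index dates run "From 1 February 2015 through 30 June 2020" and data end on 31 December 2020, so potential follow-up is about 6 to 71 months. The cited electronic-health-record study of palbociclib + AI gives medians of 49.1 and 43.2 months and HR 0.76. The cited earlier SEER-Medicare study gives HR 0.59 (SAP 2).

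**Step 1: mechanics.** With switch time S, end of time T and acceleration factor exp(psi), the counterfactual time is U = S + exp(psi) × (T - S). For illustration take exp(psi) = 0.76, censoring at 71 months and a switch at 12 months. The switcher is censored at 12 + 0.76 × 59 = 56.8 months, and a non-switcher with the same follow-up stays at 71. Re-censoring puts both at 0.76 × 71 = 54.0 months.

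**Step 2: how much censoring.** With exponential survival (rate r = ln 2 / median) and follow-up uniform on 6-71 months (assumed), the censored fraction is (exp(-6r) - exp(-71r)) / (65r).
- Median 43.2: r = 0.01605; (0.908 - 0.320) / 1.043 = 56%.
- Median 49.1: r = 0.01412; (0.919 - 0.367) / 0.918 = 60%.

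Disenrollment and HMO censoring come on top of this.

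**Step 3: the missing variance.** Writing b for the adjusted log HR, approximately Var(b) = Var(b given psi) + (db/dpsi)² × Var(psi-hat). The repeated Cox model reports only the first term.

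**Step 4: main simulation.** Assumptions: 500 patients per arm, AI median 43.2 months, follow-up uniform on 6-71 months, 400 replicates, psi estimated by inverting the log-rank test, arms comparable without weights. Selected results without re-censoring:

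| Switchers' prognosis | Switching | True HR | Mean HR | Cox SE | Actual SD | Coverage |
|---|---|---|---|---|---|---|
| Worse | 20% | 0.59 | 0.617 | 0.108 | 0.113 | 90.7% |
| Worse | 40% | 0.59 | 0.644 | 0.110 | 0.119 | 85.5% |
| Unrelated | 16% | 0.59 | 0.592 | 0.108 | 0.110 | 96.0% |
| Unrelated | 38% | 0.76 | 0.768 | 0.103 | 0.144 | 83.3% |
| Better | 15% | 0.76 | 0.757 | 0.102 | 0.116 | 90.5% |
| Better | 36% | 0.76 | 0.744 | 0.103 | 0.158 | 78.7% |
| Better | 36% | 0.59 | 0.554 | 0.111 | 0.149 | 83.3% |

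For worse-prognosis switchers with true HR 0.76, the mean HR was 0.775 at 20% and 0.787 at 41% switching. Over all patterns, Cox SE divided by actual SD was 0.87-0.98 at 15-20% switching and 0.65-0.92 at 36-41%. With psi set to its true value the ratio was 0.94-1.08, so the shortfall comes from ignoring the estimation of psi.

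**Step 5: cross-check by normal approximation.**
- Better prognosis, 36%, HR 0.76: 1.96 × 0.103 / 0.158 = 1.28, which implies about 80% coverage from the SE alone, against 78.7% simulated.
- Worse prognosis, 40%, HR 0.59: 1.96 × 0.110 / 0.119 = 1.81, which implies 93% from the SE alone. Adding the bias, ln(0.644 / 0.59) / 0.119 = 0.74, gives about 85%, against 85.5% simulated. Here bias does most of the damage.

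**Step 6: other settings** (500 vs 700 patients and AI median 40 months in the first two; all unweighted).
- Switch at 20-70% of untreated lifetime, 40% prone to switch: mean HR 0.77 for true 0.75 and 0.64 for true 0.60; coverage 91% and 87%. Under no effect, rejection was 8.3% against 4.5% for intent-to-treat (600 cohorts; Monte Carlo error √(0.083 × 0.917 / 600) = 1.1 points). With 20% prone, coverage was about 93-94.5%.
- Switch at 2-12 months regardless of prognosis: HR 0.752 and 0.753 (true 0.75), and 0.595 and 0.602 (true 0.60), at 17% and 39% switching. Coverage was 92-95% at 17% and 84-85% at 39%.
- A further run at about 30-35% switching: coverage 82-93%; null rejection 7.5-16% against 3-4% for intent-to-treat.

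**Step 7: is re-censoring alone enough?** No. In the main simulation it brought the mean HR to 0.752-0.767 (true 0.76) and 0.586-0.594 (true 0.59) in all three patterns. With the plain Cox SE, however, coverage at 36-41% switching was still 83.5-90.2% (SE 0.108-0.125 against SD 0.143-0.163).

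**The case against.** The analysis is optional, RPSFT is only an example of a method, and no decision rule hangs on it; the primary result is the intent-to-treat sIPTW comparison. That stands, and it limits the importance of the point. It does not remove it: if the method is used, the SAP says what follows, and the variance rule it inherits is incomplete.

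A reader might infer that the SAP rules out re-censoring. It does not. It says whose survival times are modified and is silent on the censoring of other AI-alone patients. What can fairly be said is that a programmer following the text would have no instruction to re-censor.

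A reader might also infer that the hazard ratio will be biased toward the null, and so will understate any benefit. The documents do not support this. That direction needs switchers to have a worse prognosis, as when switching follows progression. SAP Appendix 1 allows 60 days for a CDK4/6 inhibitor to join the regimen because coverage can be slow, so some later additions may be delayed starts unrelated to prognosis. In that case the bias was negligible, and with better-prognosis switchers it reversed.

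Two further readings go too far. This is not the only place where switching is considered: SAP 4.4 lists subsequent treatment as a possible subgroup, and SAP Table 5-2 describes switching. Nor does the SAP say that this analysis can establish significance: its weighted Cox text promises a hazard ratio and 95% CI, and a Cox P value appears only in Protocol 9.7.1. An interval that excludes 1 would still be read that way.

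Finally, re-censoring has a price. In the setting with early switching unrelated to prognosis it raised the SD, for example from 0.100 to 0.122, with no bias to remove. That is a reason to report both versions.

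**Conclusion.** The concern about the interval holds. If RPSFT is used and the SAP 7.3 Cox analysis is simply repeated, the 95% CI is too narrow: modestly at about 15-20% switching, and clearly at about 30-40%, where simulated coverage was roughly 79-93% and null rejection exceeded that of the intent-to-treat test.

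The concern about the point estimate holds as a possibility without a fixed direction. Without re-censoring the bias was toward the null if switchers do worse, about nil if switching is unrelated to prognosis, and away from the null if they do better. The largest shifts seen were 0.59 to 0.644 and 0.59 to 0.554.

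The sizes rest on assumed sample sizes, switching shares, exponential survival, uniform follow-up and a common acceleration factor. The simulated arms were comparable and unweighted, so they do not show how estimating the propensity weights would add to or offset the shortfall. This is a correction worth making before analysis; it does not touch the primary result.

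**What to change.** In SAP 7.6, replace the sentence on repeating the primary analyses with text that states:

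- how the acceleration factor is estimated;
- that the hazard ratio CI comes from a bootstrap repeating the whole procedure in each resample: propensity model and weights, acceleration-factor estimation, counterfactual times, weighted Cox model;
- that no P value is taken from the Cox model on modified times, and the intent-to-treat P value is carried forward;
- that results are shown both with re-censoring of all AI-alone patients, switchers and non-switchers alike, and without it.

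The bootstrap and the re-censoring are both needed, because neither repairs the other's fault. The cost is SAP wording and a bootstrap loop. The CI will be wider, and the re-censored version gives up some late follow-up.
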